global survey of Respite Care Providers and their respective agencies will be conducted on the use of telehealth/videoconferencing technologies to deliver individualized educational support services to families in-the-home.

Partners at Meals (experimental condition) uses the C3P Model to direct change in three key areas (place, person, PWD) whether at the RCC or in the home. In the intervention sites, project staff will train the RCC volunteers or staff members, who will train CGs to more effectively manage meals based on assessment at the Center, and will subsequently use the telehealth solution in the home. Tailoring the plan to the home is critical to family-managed sustainability. The intervention will be delivered through each CG-volunteer /staff member dyad, and each PWD-CG dyad will be enrolled for 6 months. CGs and staff/volunteers in the EUC condition will have training focused on CG needs alone for support from family and others to manage care. A comprehensive process evaluation plan will be used to monitor implementation and foster dissemination.

Specific Aims:

Aim 1: To use a repeated-measures, randomized control design to assess the relative efficacy of Partners at Meals (PaM) vs. enhanced usual condition (EUC) in terms of the following PWD outcomes at baseline, and one-month intervals: nutritional status (weight, photography of pre- and post-food consumed); dysfunctional behaviors at meals (Edinburgh Feeding in Dementia scale XL with additional fields and questions added); quality of life (QOL-AD)

Main hypothesis: Participation in PaM will be associated with improved weight maintenance and decreased dysfunctional mealtime behaviors (the latter of which is the presumed mechanism of change).

Aim 2: To assess the relative efficacy of the Intervention vs. EUC in terms of the following. CG: quality of life (Euro-QOL), burden (Zarit Burden Scale), depression (CES-D), and self-efficacy for managing meals at home; b) RCC volunteer or staff: self-efficacy for training and management of mealtime issues; c) RCC director/manager: satisfaction with the program and willingness to maintain the program post-funding.

Aim 3: Conduct a process evaluation and content analysis to assure adherence, feasibility (e.g. using the telehealth tablet at home), reach, and maintenance to inform dissemination and adoption.

Exploratory Aim 4: To assess efficacy and outcomes of PaM when research staff implements the Intervention.

B. Significance and Innovation:

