Collaborating with the 2 respite care organizations and up to 180 subjects, a cluster design will be used to determine the efficacy of the Partners at Meals (PaM) train-the-trainer program compared to enhanced usual care (EUC). Two groupings of sites will be created in attempt to balance size and racial distribution: the largest site, which is racially diverse (The ARK), will be paired with a site (in the Respite Care Charleston system), which is not diverse: Together they will be one Site for treatment condition and analysis. The other four sites in the Respite Care Charleston system that together have approximately the same diversity and size, will be joined to create a second Site. These two Sites will then be randomized to PaM and EUC. All subjects (PWD, CG and RCC volunteers) will be followed for 6 months or until discharge or voluntary termination. The biostatistician will determine the cluster randomization. An ongoing process, impact and outcome monitoring plan is planned.

We will conduct an ‘enhanced usual condition’ training to identify ways that CGs communicate with family and friends to delegate challenging aspects of caregiving. Inspired by a unit of the Savvy Caregiver, the EUC will include a 30-minute presentation at sites with a follow-up 30-minute role-play regarding identifying challenging issues, ways of communication and ways to share those elements of caregiving that could be accomplished by others. When the site ‘comes on board’, the Program Manager will deliver the training and repeated every 6

months while the project is in progress for new CGs. Additionally, the staff of the EUC sites will be included in the teaching, and will facilitate discussion with the CGs during the interim. The program staff will attend the EUC site's support group every two months (or more frequently if needed) to see if CGs need guidance and discuss issues with the EUC staff.

Further, every attempt will be made to include PWDs with similar levels of cognitive/behavioral disabilities in both the PaM and EUC conditions; however, since this is cluster design, we cannot assure an equal balance.

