Administrators/Managers at the respite sites **will be interviewed** by the Program Manager every 3 months that the study is in place for satisfaction, willingness to continue the program after completion, any CG or volunteer dissatisfaction, and are asked for data regarding discharge or hospitalization of study participants to determine if the cause could be related to nutrition-related changes. The Administrator/Manager and the project staff will ‘check-in’ every month, or more often if needed, to report any urgent problems or issues that need a timely resolution. However, the Administrators/Managers will not be consented as they are not research subjects but engaged in research (Offsite form attached) and we will be collecting feasibility and evaluation/satisfaction information from them. **Formal evaluation** of the Volunteer or RCC Staff, CG and PWD will occur at baseline, monthly and at the end of enrollment (6 months) or earlier if the CG or PWD withdraw or are withdrawn (see next section).

If requested, a step-by-step outline of the sessions used to train the Volunteer or RCC Staff, and then the CG by the Volunteer or-RCC Staff as well as ‘booster’ sessions can be provided to the IRB, as well as weekly and monthly review activities accomplished by research team members.

Measures, data sources and collection. As noted in the Aims, there are key outcome measures of interest as well as mediating and moderating variables to address secondary aims. This briefly summarizes the primary outcome measures, describes the dependent measures to address the primary study aims and summarizes all measures, collection mode and timing. **All data will be collected at baseline, monthly and when completed – at 6 months** to approximate the effect of the PaM or EUC on the groups separately and in unison. All participants at both the PaM and EUC sites will receive all measures. The primary measures against which the study is powered lie with the PWD and are **weight change and change in dysfunctional behavior**.

1. Person with Dementia measures:

Demographics collected only at baseline:

- Functional Assessment Staging Scale – level of independence in physical activities
- Mini-Mental Status Examination – rates level of dementia
- Characteristics – age, race/ethnicity, primary diagnosis/ health problems with focus on swallowing problems and possible dysphagia

Outcomes collected baseline, monthly and completion

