E. Protection of Human Subjects

1. Risk to subjects:

a. Sample

The proposed study will include 60 persons with dementia (PWD) and 60 caregivers (CGs) from 5 respite care centers (RCCs), approximately 33-57 ADC volunteers or staff and administrators/managers (will participate but are not considered subjects). The total number of persons counted for the Enrollment Tables is 180 persons. Both the PWD and his/her CG will be enrolled in this study and the PWD must attend one of the RCC sites for care at least once weekly. Additionally, volunteers will be enrolled who are long-time (defined as volunteering for at least 3 months or longer), and are present at least weekly. RCC Staff will have current affiliation with or have worked at the RCC with the last 12 months and are amenable to commit to the 6 month length of the study.

This is a cluster-randomized trial so each RCC whether in the EUC or PaM groups will be added every 2 months. For both types of conditions, the involvement of these participants includes: recruitment, consent and enrollment into the study; gathering of baseline data including an analysis of the percent of food eaten pre- and post-meals via a still photo, other assessments collected by an in-depth interview that will take about 1 hour. At this point in the **Intervention (PaM) group**, a train-the-trainer program will now be shared with RCC staff in the intervention site and within two weeks, under the direction of the Program Manager and with input from the

Registered Dietician, the RCC volunteer or RCC Staff will work with the CG to devise an initial plan of care for the PWD; this plan will be operationalized both at home and in the RCC (see Intervention – Partners at Meals). Additional training for new volunteer and booster sessions are planned. Monthly the RCC volunteer or RCC Staff and CG ‘partnership’ (dyad) will meet to determine if the plan is still working, and if adjustments need to be made with the help of the Program Manager or his/her designated staff member, and Registered Dietician, if needed. The intervention lasts 6 months and during that time, data are collected every month. Reasons for withdrawal are: death, institutionalization, and discharge from the RCC. Additionally, the administrator/manager of the RCC will be interviewed every 3 months that the project is ongoing (could be up to 2.5 years) to determine their satisfaction with the project, use of resources, and willingness to sustain the project.

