Those in the **Enhanced Usual Care (EUC) group** will have data collected at the same intervals (baseline, monthly or withdrawal) and the administrator/manager will be interviewed every 3 months. At the conclusion of the project in each site for those in the EUC sites, the Program Manager will provide the initial training sessions to the RCC volunteers at these sites.

The persons with dementia (PWD) and the caregivers (CG) could be considered vulnerable groups. Enrollment including the informed consent process and their continued participation will be based on several issues. All conversations, assessments and consenting will occur in a private room in the RCCs. The PI is very familiar with all of these sites and they all have a private room. The voluntariness of this research will be stressed every month that a CG completes their assessment; if a CG does not complete the forms requested every month after a second request, they will be asked by the Program Manager (not the RCC staff) if they consider the study to be in any way a burden, and will be withdrawn unless they state they wish to continue. PWD will be asked to assent to the Informed Consent and will be asked their assent to continue in the study every month. If at two separate times they decline, the PWD will be withdrawn from the study.

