Research materials will be obtained directly from participant in-person or telephone interviews, direct observation with checklists, and direct standing weight obtained at the RCC. Data collected directly from participants that will be recorded include social, psychological, medical, functional, and health factors related to nutritional intake, weight, and dietary intake. All information obtained will be used solely for research purposes and participant confidentiality will be assured. This will be explicitly disclosed in the Informed Consent Form and carefully reviewed with potential participants. Private information, including name, address, telephone number, and address that are individually identifiable will be collected from study participants for the purposes of this research. Such private information will be coded and each individual will be assigned a study identification number. A key will be created to decipher the code. Only the PI and Co-I, Program Manager, Research Assistant, and Registered Dietitian will have access to this code. This is because they will be contacting caregivers in their homes. Furthermore, all data will be stored in the MUSC secure REDCap database, which was used successfully in our SCTR-funded pilot study.

c. Potential risks and planned protection:

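### Default withdrawal of a caregiver for missing forms also ends the later center weights of the person with dementia, a primary outcome that needs no caregiver form

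*Combined protocol and SAP*

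**What the plan says.** **The caregiver rule.** In Section E.1.a (Sample), in the text on the enhanced usual care (EUC) group and continued participation, the trigger is "if a CG does not complete the forms requested every month after a second request". The Program Manager then asks whether the study is a burden, and the caregiver "will be withdrawn unless they state they wish to continue". Leaving is the default, and staying takes an active statement.

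**The link to the PWD.** Section D, just before the measures, schedules formal evaluation of the volunteer or staff member, caregiver and PWD at baseline, monthly and at 6 months, "or earlier if the CG or PWD withdraw or are withdrawn". Enrollment is by pair: "each PWD-CG dyad will be enrolled for 6 months" (Section A, research design). Section E.1.a says that the EUC group "will have data collected at the same intervals (baseline, monthly or withdrawal"). No section continues PWD measurement after the caregiver has been withdrawn.

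**The outcome.** Section D (Measures) names weight change as one of the two primary measures. Section E.1.b describes a "direct standing weight obtained at the RCC".

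**The PWD's own rule.** Section E.1.a asks the PWD for assent each month and withdraws the PWD after two refusals. This rule does not refer to caregiver forms.

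**Other withdrawal text.** Section E.1.a: "Reasons for withdrawal are: death, institutionalization, and discharge from the RCC". Section C (Study Overview): subjects are "followed for 6 months or until discharge or voluntary termination". Section E.2.b adds a decision by the caregiver or provider. Section C.4 of the data and safety monitoring plan adds withdrawal after certain events, with an invitation to restart.

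**The concern.** A caregiver's unreturned questionnaires say nothing about whether the PWD can be weighed. A PWD in Aims 1-3 must attend the RCC at least weekly (Section E.1.a), and weight is taken there before a meal. Ending the PWD's follow-up because of the caregiver's paperwork therefore discards primary-outcome data that could still be collected.

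The loss may not be random. An overburdened caregiver is a plausible non-responder, and burden (Zarit) is an Aim 2 outcome that the intervention is meant to change. The arms also differ in what they ask: Partners at Meals (PaM) caregivers make monthly photos and films and hold monthly planning meetings. Loss could therefore depend on both arm and outcome. The documents give no missing-data method for the trial outcomes; intention-to-treat is mentioned only for the online survey. The 5% weight-loss notification in Sections E.1.c and E.2.b also relies on weights continuing.

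**Working it through.** **1. Reading the sections together.**

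| Step | Source | Consequence |
|---|---|---|
| Forms missing after second request, no stated wish to stay | E.1.a | Caregiver withdrawn |
| Evaluation closes early if either the caregiver or the PWD is withdrawn | D | PWD's evaluation also closes |
| Enrollment is by dyad | A | No status is described for a PWD whose caregiver has left |
| Weight obtained at the RCC, before a meal | D, E.1.b | No caregiver form is needed |
| PWD assent rule is separate | E.1.a | PWD may still be attending and assenting |

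Section E.1.a on its own withdraws the caregiver. The end of PWD weights follows only once Section D is added. Section D appears to intend an evaluation at the time of leaving, so a closing weight may exist. What is lost is every later weight: a dyad that leaves at month 2 loses up to 6 - 2 = 4 monthly weights, including month 6.

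**2. Plan figures to reproduce.** None. Section D says the study is powered on the PWD measures, but the documents give no alpha, power, effect size, SD or intracluster correlation.

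**3. Precision, illustration only.** Assumptions: two-sided alpha 0.05, 80% power, equal arms, normal approximation, no clustering (although two grouped Sites are what is randomized), and 10% or 20% of PWDs lost through this rule.

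Detectable difference = (1.960 + 0.842) x sqrt(2/n per arm), in SD units.

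| PWDs lost | Evaluable | n per arm | Detectable difference | Power for 0.72 SD |
|---|---|---|---|---|
| 0 | 60 | 30 | 0.72 | 80% |
| 6 | 54 | 27 | 0.76 | 76% |
| 12 | 48 | 24 | 0.81 | 71% |

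Section D also over-enrolls by 25% and does not say whether 60 already includes this. If 25% is added to 60, then 60 x 1.25 = 75, and 75 x 0.80 = 60 remain after a 20% loss, so the precision cost is absorbed. If 60 already includes it, 60/1.25 = 48 evaluable PWDs are expected.

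**4. Selection, illustration only.** Let D be the amount by which retained PWDs do better in weight change than those lost, and p the proportion lost in an arm. The retained mean exceeds the full-arm mean by p x D. A comparison of completers is therefore shifted by D x (p in PaM - p in EUC).

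| Loss, PaM vs EUC | D = 0.3 SD | D = 0.8 SD |
|---|---|---|
| 10% vs 10% | 0 | 0 |
| 20% vs 10% | 0.3 x 0.10 = 0.03 SD | 0.8 x 0.10 = 0.08 SD |
| 25% vs 5% | 0.3 x 0.20 = 0.06 SD | 0.8 x 0.20 = 0.16 SD |

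All the rates and values of D are assumptions. Exchanging the arms' rates reverses the sign. Enrolling more dyads leaves this shift unchanged.

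**The case against.** - **The caregiver text withdraws only the caregiver.** This is literally true, and the rule alone cannot carry the point. Section D carries it to the PWD. If the sponsor means PWD weights to continue, no section says so.
- **The step is a voluntariness safeguard.** It follows a second request and direct contact by the Program Manager, and a caregiver who wishes to stay does so. One who answers that they want to leave fits voluntary termination in Section C. This stands: the burden question is sound and should remain. What is missing is a middle option, stopping the forms while the PWD is still weighed, and a sensible default for a caregiver who never answers.
- **The withdrawal lists contradict each other.** A reader might infer that Section E.1.a allows three reasons and no others. It does not say so, and the assent rule, Section E.2.b and the monitoring plan add more. The provisions are unaligned, but the omission of missed forms from one list is weak evidence of contradiction.
- **The bias favors PaM.** A reader might infer this from PaM's heavier demands. The documents do not support a direction. Both arms receive all measures and the same monthly payment, and PaM adds contact and aims to reduce burden, so the rule could remove fewer PaM dyads.
- **Repeated measures and over-enrollment cover it.** Aim 1 is a repeated-measures design, so weights up to withdrawal could be used, and no section plans the completer comparison shown above. This softens the illustration. Neither feature recovers later weights or removes loss that depends on unobserved weight change.

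**Conclusion.** The point holds for Aims 1-3. As written, the plan lets missing caregiver forms end the collection of later monthly and 6-month weights from a PWD who may still attend and assent. The loss is avoidable and plausibly related to caregiver burden.

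Its size and direction cannot be determined from the documents. Under the assumptions shown, the precision cost is modest (0.72 to 0.76-0.81 SD for 6 to 12 PWDs lost) and may be offset by over-enrollment. The shift in a completer comparison runs from 0 to 0.16 SD, in either direction. These figures show scale and are not forecasts.

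Three limits apply. A closing evaluation at withdrawal appears intended, so earlier weights are kept. The documents do not say how weight is obtained for Aim 4 participants at home, so the point does not extend to them. Nor do they say who scores the mealtime behavior scale, so the same claim is not made for the other primary measure.

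**What to change.** For Aims 1-3, revise the evaluation paragraph in Section D and the continued-participation text in Section E.1.a so that release from caregiver questionnaires is separate from withdrawal of the PWD:

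1. At the existing Program Manager contact, keep the burden question and offer the caregiver the option to stop forms while the PWD's monthly RCC weights continue to 6 months. Continue only while consent and the PWD's monthly assent remain in place and no caregiver, legal representative or PWD asks to stop.
2. State that all weights obtained, including those after caregiver forms stop, enter the repeated-measures analysis.
3. Reconcile the withdrawal provisions in Sections C, D, E.1.a and E.2.b and in Section C.4 of the monitoring plan.

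The cost is protocol wording. The consent pages are not available here, so whether the current consent covers continued weights must be checked; if it does not, consent and IRB wording is also needed. The RCC weighing is already in the schedule, so no new procedure is added.

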Due to scheduling and coordination challenges with CGs at the RCC during their normal hours of operation, we will employ both face-to-face in-person consenting as well as remote Electronic consenting.

In a private room within the RCC at a time agreeable to the potential participant, the Program Manager will describe the study protocol and informed consent in detail, including reading the informed consent form. She/he will ask the potential participant (RCC volunteer or RCC Staff, CG, and PWD if able) if he or she has any questions and if they understand the consent form. She/he will ask the participant to describe their perception of what they have read or been read in order to ensure informed consent. Extra care will be taken to ensure that the participant understands that he or she is agreeing to participate in a cluster randomized controlled trial. Care will be taken to ensure that he or she does not believe they will be receiving treatment in the study or that continued receipt RCC services is dependent upon participation in the study. Additionally, the consent form will explicitly describe that adverse health information (e.g., weight loss, possible dysphagia) related to dementia will be shared with the health provider, if the CG agrees. Past studies conducted by the PI affirm that PWD should be encouraged to assent at least monthly, and whenever possible consent to research if legally able; if not, consent will be given on their behalf by someone legally empowered to do so. Once RCC volunteers, CGs, and PWDs are consented and HIPAA forms are completed for the CG and PWD, we will randomize the sites.

Electronic or e-Consenting will be performed on eligible CGs and PWDs that want to participate in the study but are unwilling for whatever reason and/or unable to attend a face-to-face informed consent meeting at the Center. Families identified through the study recruitment processes that fall into this category will already have spoken with the researchers, have been introduced to the study and its demands, as well as had their initial questions answered. After speaking with the researchers, families that are further interested in study participation will be asked to provide an email address at which they will receive a REDCap survey link containing a scanned image of the currently approved Informed Consent document (developed from the MUSC REDCap e-consent template). Families will be able to take as much time as they like to read the consent document together in the comfort and privacy of their own home or at a place and time of their choosing. Prior to providing their physical e-consent, the researchers will coordinate with these families; so as to be on the telephone and be available to further answer any questions that they may have during the e-consent process. Should a participant have any questions or concerns about the study, the researchers will address these issues to the best of

their abilities and knowledge. Upon submitting the e-consent, a REDCap trigger will immediately notify the researchers, who will then provide their countersignature to the document.

Participants will be able to download a copy of their executed informed e-consent/HIPAA authorization forms directly to their own computer, or have copies emailed to them. They will also be given the option to have a copy of their executed e-form mailed to them should they elect to do so. A copy of the executed e-consent will also be stored in the participant's electronic case record for monitoring and audit purposes.

b. Protection against risks including confidentiality:

Risks to confidentiality will be protected by coding participant records as described above. Additionally, all study participant records will be kept in the secure REDCap System – “a mature, secure web application for building and managing online surveys and databases. All transactions are securely delivered to the application using SSL (SHA-1th RSA Encryption;; 2048-bits). It is then transmitted internally (behind the MUSC firewall to the database server.) All transactions are logged at the server layer (http logging), application layer (REDCap logs activity to a database table), and the database layer (using both query and binary logging.) Whenever possible, all data entry will be made directly into tablets fitted with the REDCap secure application.” Any signed documents will have the signature page scanned and uploaded into REDCap. A separate Regulatory Binder will also be kept in a locked cabinet in the PI’s (TK) locked office.

Regarding protection against other forms of risk (psychological, physical, social, etc.), several safeguards will be in place. If at any time during any interaction with study staff, a participant exhibits or expresses burden or fatigue, the session will be interrupted and arrangements will be made to resume at a later date. If any of the CGs report a level of burden of depression that is considered serious, we will ask them to report this to their healthcare provider as soon as possible or offer to make the report with their permission. If a PWD’s weight is reduced by 5% or greater, or displays increased agitation during the intervention, we will inform the CG and ask to inform their healthcare provider. The PWD will be withdrawn from the study if the CG or the provider decide this is the best course.

c. Payment to participants:

As noted in Section 1.a - All CGs enrolled in the study, whether in the PaM or EUC arm, will receive \$50 per month for every month they are enrolled in the trial. It is expected that since the CGs live with or on the same property as the PWD, that this money will be considered shared. RCC volunteers receive \$100 for every CG they partner with – this will be paid at the conclusion of the volunteer training (\$50) and another \$50 after the third month of pairing with each Caregiver. Administrator/managers will not receive any direct reimbursement. We support a community-engagement approach to research and have always shared our funding with our community partners based on an estimate cost to the agency.

3. Potential Benefits of the Proposed Research to the Subjects and Others:

The benefits to participants of participating in the study are that PWD may increase caloric intake and stabilization or increase in weight. Their interaction with the CG and RCC volunteer

or RCC Staff at meals may improve their QOL. This may result in prevention of unintentional weight loss, improved function, reduced morbidity and mortality, and decreased adverse outcomes, including morbidity, institutionalization, and mortality. The benefit to others is that if this program is proven effective, other PWDs and CGs might benefit as well from its future implementation. The intervention could result in improved mental health and QOL of CGs, and the ability of RCC staff to influence the knowledge, skills and behaviors of CGs and PWDs on other issues. Administrators/managers could better manage problem issues and consider the use of tele-health as a meaningful way of communicating and assisting clients.

4. Importance of Knowledge to be Gained:

Information gathered from this study could lend support to policies designed to enhance the nutritional status of PWD, and mental health indicators of their CGs; it could provide a valuable way to increasing knowledge and skills of CGs and use RCCs as a mechanism to offer more integrated training and treatment in their facilities. Information gathered in this study could be used by foundation and organizations serving PWD such as the Alzheimer's Association, the Brookdale Foundation or various state agencies that deliver care to older adults such as the Lieutenant Governor's State of South Carolina Office on Aging to disseminate training programs specifically for community-based programs. The minimal risks involved in this study are reasonable in relation to important information that a non-invasive cost-effective intervention might provide.

a. Dissemination plan:

The investigators of this study plan to share the results with appropriate audiences – both scientific and community based. We plan to submit abstracts to the following conferences (at least 1 annually):
1) Gerontological Society of America (November)
2) International Academy on Nutrition and Aging on Nutrition and Alzheimer's Disease (July)
3) American Association of Public Health (November)
4) Academy of Nutrition and Dietetics (October/November)
5) Alzheimer's Association Annual Meeting (July)
6) Local conferences that involve community organizations and ethnic/minority communities

Planned publications include:

- 1) The Gerontologist
- 2) The Journals of Gerontology: Health Sciences
- 3) Journal of Nutrition, Health & Aging
- 4) Journal of Applied Gerontology
- 5) Journal of Clinical Bioinformatics
- 6) Journal of Telemedicine and Telecare

The material resources used for this study (Train-the-Trainer Manual, videos, brochures, PowerPoint presentations, "Playbooks") will be shared with the community and academic partners, NIH, and the general public. Findings from this study will be disseminated and shared with community and academic partners, NIH and the general public via professional and lay publications, presentations and forums, web-sites, newsletters, or other mechanisms.

References (key – full list of 101 references can be furnished)

Administration on Aging. A Profile of Older Americans: 2014. Washington DC: US Department of Health and Human Services; 2014 [15].

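### A weight loss of 5% can lead to a PWD leaving the study, which ends follow-up on a primary measure; the likely effect is small and the remedy cheap

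*Combined protocol and SAP*

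**What the plan says.** All references are to the combined protocol and SAP.

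- **Trigger and consequence (E.2.b, *Protection against risks including confidentiality*).** If a PWD's "weight is reduced by 5% or greater, or displays increased agitation during the intervention", the CG is told and the provider is to be informed. The section then states: "The PWD will be withdrawn from the study if the CG or the provider decide this is the best course." The withdrawal is from the study, not only from the intervention.
- **Primary measures (D, *Measures, data sources and collection*).** "The primary measures against which the study is powered lie with the PWD"; they are weight change and change in dysfunctional behavior.
- **Last assessment.** In section D, formal evaluation is at baseline, monthly and at 6 months, "or earlier if the CG or PWD withdraw or are withdrawn". In E.1.a the EUC group "will have data collected at the same intervals (baseline, monthly or withdrawal").
- **Length of follow-up (C, *Study Overview*).** Subjects "will be followed for 6 months or until discharge or voluntary termination".
- **Related text.** The list of withdrawal reasons in E.1.a has death, institutionalization and RCC discharge, but not weight loss. E.1.c treats a loss above 5% as a reason to contact the CG and says nothing of withdrawal. Section C.4 of the Data and Safety Monitoring Plan gives, as an optional step in an adverse-event example with less than 5% loss, withdrawal with an invitation to restart later.

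**The concern.** The PWDs who lose most weight are the ones who may stop being weighed. Aim 1 is "To use a repeated-measures, randomized control design to assess the relative efficacy" of the two conditions on monthly outcomes, so the month-6 comparison needs to know what happened to those PWDs. A repeated-measures analysis that includes the withdrawal weight copes well if weight keeps the same course afterwards. That is open to doubt here, because the same event directs the PWD to a healthcare provider and withdrawal ends the sessions. Only later weights can show whether the loss stopped, reversed or sped up.

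The rule also ends two things at once, the intervention and the measurement, although only the first may be needed to protect the PWD. The agitation trigger raises the same issue for mealtime behavior, though agitation is a related sign and not the scale itself.

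**Working it through.** **Step 1: does other text cancel the rule or schedule later weights?** The E.1.a list omits weight loss, and E.1.c asks for notification only. Both sit uneasily with E.2.b, but neither says that a PWD withdrawn under E.2.b stays in follow-up. The restart invitation is optional and does not provide for weighing withdrawn PWDs. No section separates stopping the intervention from stopping follow-up. Intention-to-treat is named only for the online survey. The gap stands.

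**Step 2: inputs.** From the documents: 60 PWDs, monthly weights, 6 months, 5% threshold. There is no stated SD, effect size, power or ICC, so there is no figure of the plan's own to reproduce. Assumed:

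- 30 PWDs per arm;
- mean 6-month change of -2% in EUC and 0% in Partners at Meals (PaM), a true difference of 2.0 points;
- SD of 6-month change 4% (range 3% to 5%);
- percent change at month t = slope × t/6 + N(0,1), with slope SD = √(SD² − 1);
- a PWD is flagged at the first weight at or below -5% in months 1 to 5, and is then withdrawn with probability w.

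The agitation trigger is not modelled.

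**Step 3: numbers flagged.** Simulation with 1,000,000 PWDs per arm, scaled to 30 per arm, gives 7.6 of 60 flagged at SD 4% (about 4 at SD 3%, 11 at SD 5%). With w = 0.25, 7.6 × 0.25 = 1.9 PWDs are withdrawn.

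**Step 4: estimated difference (true value 2.0, SD 4%).**

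| Share of flagged withdrawn | 10% | 25% | 50% | 100% |
|---|---|---|---|---|
| Completers only | 1.95 | 1.88 | 1.74 | 1.41 |
| Withdrawal weight carried forward | 1.98 | 1.95 | 1.90 | 1.81 |

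**Step 5: error of a random-slope mixed model on weights up to and including withdrawal.** The target is the true month-6 difference by assigned condition.

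| Course after withdrawal | 10% | 25% | 50% | 100% |
|---|---|---|---|---|
| Unchanged | 0.00 | 0.00 | 0.00 | 0.00 |
| Loss stops | +0.03 | +0.07 | +0.13 | +0.26 |
| Loss reverses | +0.05 | +0.13 | +0.27 | +0.53 |
| Loss doubles | -0.03 | -0.07 | -0.13 | -0.26 |

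The model in effect projects the earlier course to month 6, so its error is the between-arm difference in the part of the course that changed. At w = 0.25 with SD 3% to 5%, the errors are 0.04 to 0.18 in size.

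**Step 6: scale.** SE = 4 × √(2/30) = 1.03, ignoring clustering. At w = 0.25, 0.07/1.03 is about 7% of the SE and 0.13/1.03 about 13%.

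**Step 7: weights lost.** The mean is 1.75 per withdrawn PWD, and at most 5 (flagged at month 1). Over all withdrawn PWDs this is 7.6 × 1.75 = 13.3 at w = 1, and 1.3 at w = 0.1.

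**The case against.** The strongest reply is that this is too small to matter. About 2 PWDs are involved at the 25% share, the error is a small fraction of the SE, and monthly payment while enrolled (E.2.c) favours staying. The larger errors need nearly every flagged PWD to be withdrawn. This stands, and it is why the point is a cheap improvement and not a serious flaw.

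A second reply is that the error in Step 5 exists only if the target is the effect by assigned condition whatever happens after withdrawal, and only if weight then changes course. The documents state neither. PaM also aims for the CG to take the lead in planning, so its effect may outlast the sessions. This stands as a limit on the size. It does not answer the gap, since without later weights nobody can tell.

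A third reply is that, read with E.1.a and E.1.c, the sentence may do little more than respect a family's choice to leave. That is a fair reading of intent, but the wording still ends study participation.

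A reader might also infer several stronger things, which the documents do not support:

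- *That a 5% loss means automatic withdrawal.* The CG or provider must decide.
- *That the triggering weight is lost.* An assessment at withdrawal is planned in both arms.
- *That only completers will be analysed.* No such analysis is proposed.
- *That withdrawal will differ by arm and favour PaM.* Training does differ ("CGs and staff/volunteers in the EUC condition will have training focused on CG needs alone"), but nothing shows that this changes the decision. With no true effect (both arms -1%, SD 4%) and 25% of flagged PWDs withdrawn in PaM only, the spurious difference is +0.18 for completers and +0.03 with the withdrawal weight carried forward.

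**Conclusion.** The concern holds in a limited form. E.2.b lets a primary outcome, or a sign related to one, end its own follow-up, and no assessment is planned after withdrawal. On the assumed inputs the likely error is about 0.07 to 0.13 points on a true difference of 2.0 at 25% withdrawn, and zero if the course is unchanged. Its sign depends on the later course of weight, so the documents fix neither its size nor its direction. The case for acting rests on low cost and avoidability, not on a large bias. Confidence is medium, because every weight input is assumed.

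**What to change.** In E.2.b and the consent form, state that a decision by the CG or provider after such a flag stops the intervention or EUC contact only. Monthly weights then continue to month 6, with CG agreement and PWD assent, for PWDs still attending the RCC. Where the CG is willing, continue the EdFED as well, since the agitation trigger bears on the second primary measure. For Aim 4 PWDs who do not attend an RCC, continue weights by whatever method is already used for them.

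State that a PWD or CG may still leave fully at any time. The E.1.a rules on uncompleted CG forms and twice-declined assent stay as they are. Analyse every weight obtained, including the withdrawal weight, under the assigned condition. Align E.1.a and E.1.c with the revised rule.

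Cost: about 2 further weights per withdrawn PWD, at most 5. For those attending, these are standing weights at the RCC (E.1.b), where enrolled PWDs come at least weekly (E.1.a); continued attendance after a flag is not guaranteed. If the CG payment continues, the cost is 1.75 × $50 = $87.50, about $90 per withdrawn PWD, and at most 5 × $50 = $250. The change does not address the separate limit that each condition is one composite Site (C, *Study Overview*).
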